7.7.4.2 Vital Signs

Observed values at each visit and change from baseline values for vital sign measurements will be summarised descriptively by treatment group. All vital sign measurement data will be listed.

7.7.4.3 Clinical Laboratory

Observed values at each visit and change from baseline values for clinical laboratory evaluations will be summarised descriptively by treatment group. Additionally, shift tables will be presented for chemistry and hematology parameters from baseline to each post-baseline assessment. All clinical laboratory data will be listed.

7.7.4.4 Intra-Ocular Pressure

All IOP data will be listed. Observed values at each visit and change from baseline values for IOP evaluations will be summarised descriptively by treatment group for the study eye and non-study eye.

7.7.4.5 Slit-Lamp Biomicroscopy and Ophthalmoscopy

Ocular findings will be evaluated by the following criteria:

- Normal
- Abnormal (NCS)
- Abnormal with clinical significance (CS)

Data from all slit-lamp biomicroscopy and ophthalmoscopy assessments will be listed. The number and percentage of patients with at least 1 treatment-emergent CS abnormality by ocular assessment will be summarised for each treatment group for the study eye and non-study eye. An abnormality will be deemed treatment-emergent if the onset date is on or

after the date of first treatment. A patient will be counted once even if the patient experiences more than 1 treatment-emergent CS abnormality.

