(compiled from multiple papers), 31 (65%) out of 47 cases eventually achieved a clear cornea, with healing taking place as early as 1 month after the procedure (Van den Bogerd et al 2018). If there was persistent oedema at 6 months, then it was unlikely to resolve. If corneal oedema did not clear, some patients' corneas cleared without residual stromal damage after DMEK performed as rescue therapy between 4 and 8.5 months after Descemet's membrane stripping (Van den Bogerd et al 2018). All keratoplasty procedures, including DMEK, are associated with risks of graft detachment, graft failure or immune rejection. There is a medical need for medication that can speed healing after descemetorhexis and that can help establish a high, functional ECD to maintain corneal transparency.

Ripasudil ophthalmic solution 0.4% (K-321) is a Rho-associated protein kinase (ROCK) inhibitor that has been marketed in Japan since December 2014 as Glanatec[®], with twice daily (BID) dosing for glaucoma and ocular hypertension. Studies in endothelial cells have indicated that K-321 can lead to reduction of apoptosis, enhancement of cell proliferation, and increased rates of migration, all of which may support endothelial healing (Kowa Company Ltd 2019). Moloney et al (2017) first reported use of a ROCK inhibitor to promote healing in patients with FECD treated with Descemet stripping only (DSO). More recently, Macsai et al (2019) reported results from a small study of 18 patients with FECD and central confluent guttae of up to 5 mm diameter who underwent DSO and were subsequently treated with either ripasudil ophthalmic solution 0.4% four times daily (QID) or no ripasudil for 2 months. Overall, patients who underwent DSO with ripasudil recovered vision more quickly [REDACTED]

[REDACTED] The patients in the no-ripasudil group had [REDACTED] while in the ripasudil group there was [REDACTED]. In the short-term studies (8 weeks duration and less) for the development of Glanatec, there were [REDACTED]

[REDACTED]
[REDACTED]
[REDACTED] (Kowa Company Ltd 2019).

Kowa proposes to pursue development of K-321 (ripasudil ophthalmic solution) for the following indication: “the treatment of Fuchs endothelial corneal dystrophy after descemetorhexis.” This will be the first Kowa-sponsored study in patients for this indication.

2 Study Objectives

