Except on days of study visits on Day 1 through Week 12 (not including Visit 9) during the treatment period, study drug will be dosed by the patient QID (Section 5.2): morning (9 AM \pm 1 hour), mid-day (1 PM \pm 1 hour), evening (5 PM \pm 1 hour), and night (9 PM \pm 1 hour). Each patient will be provided with 2 sets of colour-coded [REDACTED], one set to be applied

morning and night (M/N) and the other to be applied mid-day and evening (MD/E). See Section 5.4.1 for a detailed description of packaging.

On study visit days Visit 3 through Visit 9, patients will not apply any study drug until after all study measurements have been completed; thereafter on those days, patients will start dosing with the dose closest in timing to the dosing regimen and continue with the remaining doses for the day. Additionally, on Visit 3 they must first apply the study drug within [REDACTED] after the end of the descemetorhexis procedure on Day –1 (Visit 2).

With the primary efficacy endpoint being assessed at Visit 9 (Week 12), if a patient applies any study drug on the day of Visit 9 before all study measurements have been completed, that patient's Visit 9 should be rescheduled within the visit window allowance (eg, the next day). For visits other than Visit 9 during the treatment period, a patient who applies study drug before all study measurements have been completed will be assessed as planned, and a protocol deviation must be recorded.

At Visit 9 (Week 12), patients will enter the drug-tapering phase of the follow-up period, and new study drug will be dispensed without M/N or MD/E colour coding (Section 5.2). All patients will self-administer their tapering-phase study drug BID (9 AM \pm 1 h and 9 PM \pm 1 h) for a week, then once daily (9 AM \pm 1 h) for a week, and then will discontinue study drug. At Visit 9, patients will apply the first dose of study drug [REDACTED] of completing study measurements and will apply the second dose at night, as scheduled.

During the follow-up period, patients will attend 5 study visits (Figure 3-1), starting at Week 16 (Visit 10).

Study activities and assessments will be performed at study visits as described in Table 6-1 and in Section 6. [REDACTED] will determine central ECD by analysing digital images of the corneal endothelium (Table 11-1).

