5.5 Medication Errors

At Visit 3, patients will be given instructions on how to administer their assigned ophthalmic solution and how to avoid contaminating the [REDACTED] solution, and they will be observed instilling their own drops by the site staff. Re-education on the proper administration procedure will be given to patients by study site staff throughout the treatment period at each visit. To minimise medication errors during the 12-week treatment phase, [REDACTED] and [REDACTED] will be colour-coded differently for M/N and MD/E doses.

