6.1.2 Descemetorhexis of the Study Eye

Each patient will undergo descemetorhexis of the investigator-selected study eye at Visit 2 (Day -1). A digital photo of the study eye must be taken immediately before and immediately after descemetorhexis at Visit 2. The investigator will perform descemetorhexis to remove central confluent guttae, removing an area of Descemet membrane with a diameter of [REDACTED]. The longest diameter and the shortest diameter must be recorded in the eCRF. The procedure must be recorded by video to record potential differences in technique among investigators. Also, immediately after the operation, the stripped area will be recorded by photo or video with an adjacent scale to measure the area removed. Detailed guidance for performing the study eye descemetorhexis will be provided in the study manual.

Recommended post-descemetorhexis concomitant therapy is described in Section 5.8.1.

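### The date-only rule in Protocol 7.7.4.5 counts a surgical corneal finding dated at the pre-dose Day 1 slit-lamp as treatment-emergent, contrary to the protocol's own exposure-based definition

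*Protocol*

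**What the plan says.** Protocol 7.7.4.5 grades ocular findings as normal, abnormal but not clinically significant (NCS), or CS. It then describes one summary, for the study eye and the non-study eye: "The number and percentage of patients with at least 1 treatment-emergent CS abnormality by ocular assessment will be summarised for each treatment group". On counting: "A patient will be counted once even if the patient experiences more than 1 treatment-emergent CS abnormality". On emergence: "An abnormality will be deemed treatment-emergent if the onset date is on or" after the date of first treatment. The rule sets no clock time, makes no comparison with an earlier grade and has no clause for worsening. All slit-lamp data are also listed.

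The order of events is fixed elsewhere in the protocol:

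- Surgery (6.1.2): "Each patient will undergo descemetorhexis of the investigator-selected study eye at Visit 2", which is Day -1.
- Slit-lamp (Table 6-1): the Visit 2 examination is footnoted as pre-operative. The next is Visit 3, Day 1.
- Dosing (3.1 and 5.2): on visit days from Visit 3 to Visit 9, "patients will not apply any study drug until after all study measurements have been completed". Visit 3 is also when dosing starts. Study drug is first dispensed and administered there in Table 6-1, and 5.5 says "At Visit 3, patients will be given instructions on how to administer their assigned ophthalmic solution", with staff watching the patient instil the drops.

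Section 6.3.2.1 defines a treatment-emergent adverse event differently. The event must be absent before exposure to study drug, or already present and then worse in intensity or frequency after exposure.

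**The concern.** Every study eye has had part of Descemet's membrane removed the day before dosing, so some corneal abnormality at the Day 1 slit-lamp is to be expected. A finding seen then cannot be due to study drug. If its onset is recorded as Day 1, the date rule still labels it treatment-emergent, because examination and first dose share a calendar date. The once-per-patient rule then closes that eye's entry: a CS corneal finding that arises on drug weeks later no longer changes the count.

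At stake is how readable one descriptive safety table is. A secondary objective (2.2) is safety at each visit out to 52 weeks. A count partly filled by surgical findings is less able to show a later excess on K-321.

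**Working it through.** **Step 1: timing.** Surgery (Day -1), then Visit 3 slit-lamp (Day 1, before dosing), then first dose (Day 1). The date of first treatment is Day 1.

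**Step 2: the two rules applied to the same finding.** Take a CS corneal finding caused by surgery and first seen at the Visit 3 slit-lamp.

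| Case | 7.7.4.5 | 6.3.2.1 definition |
|---|---|---|
| Onset recorded as Day 1 | Emergent (Day 1 is on the date of first treatment) | Not emergent (present before exposure) |
| Onset recorded as Day -1 | Not emergent | Not emergent |
| NCS at Visit 3, CS later | Depends on whether onset means first appearance or the date it became CS | Emergent (worsened after exposure) |

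The rules disagree in the first row, and 7.7.4.5 gives no firm answer in the third.

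**Step 3: size of the dilution.** The plan states no figure for this display, so there is none to reproduce. Let s be the share of eyes with a CS surgical finding dated Day 1. It is equal across arms in expectation, since it precedes dosing. Let p be the chance of a later CS finding, taken as independent of the Day 1 finding.

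- Ever-rate per arm = s + (1 - s)p.
- Displayed gap = (1 - s)(p_drug - p_placebo).

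Neither s nor p is in the documents. As an assumption, take p = 40% on drug and 10% on placebo (a true gap of 30 points) with 20 patients per arm (7.4).

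| s | Ever-rate, drug vs placebo | Displayed gap (points) |
|---|---|---|
| 0% | 40.0% vs 10.0% | 30.0 |
| 10% | 46.0% vs 19.0% | 27.0 |
| 34% | 60.4% vs 40.6% | 19.8 |
| 50% | 70.0% vs 55.0% | 15.0 |
| 95% | 97.0% vs 95.5% | 1.5 |

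**Step 4: what a Visit 3 reference can recover.** CS is the top grade, so an eye still graded CS from surgery cannot show a second finding by grade. Let c be the share of Day 1 CS eyes that drop below CS before the later finding. With the Visit 3 reference:

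- Displayed gap = (1 - s + sc)(p_drug - p_placebo).

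At s = 34%:

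- c = 0: 0.66 x 30 = 19.8 points, the same as under the current rule.
- c = 0.5: (0.66 + 0.17) x 30 = 24.9 points.
- c = 1: 30 points.

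The exact binomial chance of at least 4 more affected patients on drug, 20 per arm, shows the same limits:

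| s | Current rule | Visit 3 reference, c = 0 | Visit 3 reference, c = 1 |
|---|---|---|---|
| 10% | 0.751 | 0.777 | 0.836 |
| 34% | 0.563 | 0.576 | 0.836 |

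If no surgical finding clears, the change gains almost nothing. The 0.836 is an upper limit.

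**The case against.** **Onset is not the examination date.** A purely surgical finding arguably began on Day -1, and if sites record it so, it is excluded already. This stands: the effect is then nil. But 7.7.4.5 does not say how onset is dated, and about 30 sites could differ.

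**6.3.2.1 already supplies the right definition.** Only in part. It defines adverse events. Section 7.7.4.5 states its own rule, and 7.7.4.1 restates the date-only version for the adverse event tables.

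**The cornea is followed in other ways.** This stands. Oedema, thickness and clearance are analysed by visit (7.2, 7.7.2). Clinically important findings become adverse events, which are summarised by period, with ocular events shown by eye (7.7.4.1). All slit-lamp data are listed for about 60 patients. A reader might infer that late corneal harm would go unseen; the documents do not support that.

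**By ocular assessment may mean per examination, not per structure.** Possible. That reading pools more findings into one count, so the same fault remains.

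**Primary SAP v2.0 is not among the documents.** The SAP addendum (section 1) says it does not repeat that plan's analyses, and Protocol 7.7 leaves data conventions to the SAP. So the point is limited to 7.7.4.5 as written.

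**Two stronger readings are tempting.** One is that the arm comparison is biased. It is not: surgery and the Day 1 examination precede dosing, and randomisation follows surgery. The other is that a definite loss has been shown, such as 0.836 falling to 0.563. It has not. The nearest figures in the protocol are the roughly 10% assumed unmeasurable at Week 12 because of oedema (7.4), and the 16 of 47 published cases (34%) left after "31 (65%) out of 47 cases eventually achieved a clear cornea, with healing taking place as early as 1 month after the procedure" (section 1). Both describe persisting oedema, not a Day 1 CS grade, and persisting eyes are the ones that the change cannot help.

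**Conclusion.** The point holds, as a minor one. As written, 7.7.4.5 labels a pre-drug surgical finding dated Day 1 as treatment-emergent, and that label conflicts with 6.3.2.1. The consequence is dilution by the factor (1 - s) of a count that carries no hypothesis test (7.7.4). The primary analysis is untouched.

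The size is unknown. It rests on how often Day 1 surgical findings are graded CS and dated Day 1, and on later findings being independent of them. It runs from nil (s = 0, or onset dated Day -1) to near-total loss of contrast if almost every eye is graded CS on Day 1. The recoverable part is confined to eyes whose surgical finding clears or falls below CS before the later one.

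**What to change.** In 7.7.4.5, for the study-eye cornea, make the pre-dose Visit 3 slit-lamp the reference. Findings present then count as treatment-emergent only if they worsen (for example NCS to CS) or recur after clearing. This brings the section into line with 6.3.2.1. Stating how onset is dated would close the remaining gap.

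Optional: split the count by period, as is done for adverse events, into Visits 4 to 9 and Visits 10 to 14. Section 3.1 says "During the follow-up period, patients will attend 5 study visits", starting at Week 16. No scheduled slit-lamp falls inside the Week 12 to 14 taper, so the taper would be merged with follow-up.

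If primary SAP v2.0 already does this, cite it in 7.7.4.5 instead.

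Cost: one sentence and a re-derived flag, from data already collected. Eyes still graded CS from surgery would still need the listing.

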4.1.1 Inclusion Criteria

Each patient must meet all of the following criteria to be enrolled in this study:

1. Is at least 18 years old at the screening visit (Visit 1). – Re-screening possible if initial screening was soon before 18th birthday.
2. Has a diagnosis of FECD at Visit 1. – Rescreening is not possible.
3. Has confluent central guttae in the study eye that can be removed by descemetorhexis of a circular area of [REDACTED] diameter or less (at Visit 1). – Rescreening is not possible.
4. Has a study eye with best corrected visual acuity (BCVA) of 75 letters or fewer by Early Treatment Diabetic Retinopathy Study (ETDRS) testing (Snellen equivalent of 20/32 or worse) at Visit 1. – Rescreening is not possible.
5. The study eye descemetorhexis at Visit 2 is confirmed to have excised a central area with confluent guttae and a diameter of [REDACTED]. Guidance for performing the study eye descemetorhexis and measurement of the excised area will be provided in the study manual. – Rescreening is not possible in that eye but the non-study eye can be used.

6. Can understand the written informed consent, provides signed and witnessed written informed consent, and agrees to comply with protocol requirements before any study-specific assessment is performed. – Rescreening is not possible.

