6.3.2 Adverse Events

6.3.2.1 Definitions of Adverse Events

An AE is defined as any untoward medical occurrence in a patient enrolled into this study regardless of its causal relationship to study drug. An AE can therefore be any unfavourable and unintended sign (including an abnormal laboratory finding), symptom, or disease temporally associated with the use of a medicinal product, whether or not considered related to the medicinal product. Patients will be instructed to contact the investigator at any time after randomisation if any symptoms develop.

An AE may include the following:

- Exacerbation of a pre-existing disease or symptom
- Increase in frequency or intensity of a pre-existing event or condition
- A condition detected or diagnosed after study drug administration even though it may have been present prior to the start of the study

An AE does not include the following:

- Medical or surgical procedures (although the condition that leads to the procedure must be reported as an AE)
- Pre-planned medical procedures (eg, planned surgical interventions, investigations, social and/or convenience hospitalisations)
- Pre-existing disease or conditions present at the time of signing the ICF are considered concurrent medical conditions and must not be recorded as an AE

The investigator must attempt to establish a diagnosis of the event based on signs, symptoms, and other clinical information. In such cases, the diagnosis must be documented as the AE and not as the individual signs or symptoms.

The investigator will evaluate any changes in laboratory values and other study investigations and determine whether the change is clinically important and whether it is related to the study drug. The investigator must record the AE or investigation abnormality in the eCRF regardless of the relationship to the study drug (ie, the AE will be recorded whether or not it is considered related to the study drug).

Considerations for determining whether an abnormal objective test finding must be reported as an AE may include whether or not::

- The test result is associated with accompanying symptoms
- The test result requires additional diagnostic testing or medical/surgical intervention
- The test result leads to a change in study drug dosing or discontinuation from the study, significant additional concomitant drug treatment or other therapy and/or
- The test result leads to any of the outcomes included in the definition of an SAE

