Merely repeating an abnormal test, in the absence of any of the above conditions, does not require reporting as an AE. An abnormal test result that is determined to be an error or artefact does not require reporting as an AE.

A treatment-emergent AE (TEAE) is defined as any event not present before exposure to study drug or any event already present that worsens in either intensity or frequency after exposure to study drug.

An SAE is defined as any event that

- results in death.
Any death resulting from an AE occurring during the study period or within 30 days after the last dose of the study drug, even if the death appears to be completely unrelated to the study or study drug.

- is immediately life threatening.
The term ‘life-threatening’ refers to an event in which the patient was at risk of death at the time of the event; it does not refer to an event that hypothetically might have caused death if it were more severe.
- requires inpatient hospitalisation or prolongation of existing hospitalisation.
The term ‘hospitalisation’ means a hospital admission or an overnight stay; prolongation means delay of a planned or anticipated discharge date by at least 1 overnight stay. Adverse events which require attendance at hospital but do not require admission may be considered medically important.
- results in persistent or significant disability/incapacity.
- results in impairment, damage, or disruption in the study patient’s body function or structure, or physical ability or quality of life.
- is a congenital anomaly/birth defect.
Additionally, events in which there is suspicion that exposure of either parent to the study drug resulted in an adverse outcome in the offspring is a medically important event.
- Is medically important: an event that may not be immediately life-threatening or fatal or result in hospitalisation, but may require intervention to prevent one of the serious outcomes listed above.
Examples of such events are intensive treatment in an emergency room or at home for allergic bronchospasm; blood dyscrasias; convulsions that do not result in hospitalisation; or development of drug dependency or drug abuse.

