6.3.2.3 Reporting Adverse Events

All AEs reported or observed will be recorded on the AE page of the eCRF. Information to be collected includes event term, time of onset, date of resolution of the event, seriousness, severity, relatedness to study drug, any required treatment or evaluations, and outcome.

The investigator will assess the severity of the event. The severity (intensity) of AEs must be classified using the following criteria:

- **Mild:** An AE that is easily tolerated by the patient, causes minimal discomfort, and does not interfere with everyday activities
- **Moderate:** An AE that causes enough discomfort to interfere with normal everyday activities and may require intervention
- **Severe:** An AE that prevents normal everyday activities (treatment or intervention will usually be required). Severe events are usually incapacitating

When changes in the severity of an AE occur more frequently than once a day, the maximum intensity for the event must be noted for that day. Any changes in intensity of signs and symptoms over multiple days will be captured by recording new AEs, with the amended intensity grades and the dates (and time, if known) of the change(s). Changes in the intensity

of an AE must be documented to allow an assessment of the duration of the event at each level of intensity.

The investigator will assess the causal relationship between the study medication and the AE and decide whether, in his or her qualified medical judgement, there is a reasonable possibility that the event may have been caused by the study drug. There are 2 categories of causality:

- **Unrelated:** If no valid reason exists for suggesting a relationship, or the event may plausibly be related to the patient's clinical condition, an underlying disease or other medication taken by the patient, then the AE must be considered unrelated.
- **Related:** If there is any valid reason for supposing that there is a relationship between the study medicine and the AE, especially if the event improves on withdrawal of the drug (de-challenge) or recurs on recommencement of therapy (re-challenge), then the AE must be considered related. The AE must not be considered related simply because it is not possible to rule out an association between the AE and the study drug.

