7.7.4.1 Adverse Events

All AEs will be listed and all TEAEs will be summarised. Adverse events will be deemed treatment-emergent if the onset date is on or after the date of first treatment. Events which are not treatment-emergent will be listed separately and together with all other AEs. AEs will be summarised separately for the treatment period, the tapering phase, and the 9-month follow-up period. Ocular TEAEs will be summarised separately from non-ocular TEAEs. Ocular TEAEs will be summarised separately for the study eye and non-study eye.

Treatment-emergent AEs will be summarised by treatment group, presenting the number and percentage of patients having a TEAE in each system organ class and having each individual TEAE based on the preferred term. Treatment-emergent AEs will also be tabulated according to intensity and causality. Patients who experienced multiple TEAEs for a preferred term will be counted once, similarly for patients with multiple TEAEs per system organ class.

Deaths, SAEs, and TEAEs leading to discontinuation of study treatment will be listed separately and, if appropriate, summarised by treatment group, system organ class and preferred term.

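### Section 7.7.4.5 dates treatment-emergent ocular findings by an undefined onset and has no worsening limb, so an NCS finding that becomes CS on drug may be left out of the summary

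*Protocol*

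**What the plan says.** Protocol section 7.7.4.5 places each ocular finding in one of three grades: normal, abnormal NCS, or abnormal CS. The planned summary, by treatment group and separately for study and non-study eye, is this: "The number and percentage of patients with at least 1 treatment-emergent CS abnormality by ocular assessment will be summarised". Treatment-emergent is defined by date alone: "An abnormality will be deemed treatment-emergent if the onset date is on or" after the date of first treatment. Ungrouped data appear only as a listing: "Data from all slit-lamp biomicroscopy and ophthalmoscopy assessments will be listed".

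For adverse events, section 6.3.2.1 gives a wider meaning. A TEAE is an event absent before exposure, or "any event already present that worsens in either intensity or frequency after exposure to study drug". Section 7.7.4.1, which governs the AE tables, goes back to a date rule: "Adverse events will be deemed treatment-emergent if the onset date is on or after the date of first treatment".

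**The concern.** NCS is itself a grade of abnormal. A finding graded NCS at screening therefore already has an onset before treatment, on the ordinary meaning of the word. If it becomes CS during dosing, the date rule classes it as not treatment-emergent and the patient does not enter the count.

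This matters more here than in most trials because the treated tissue is abnormal at entry by design. Inclusion criterion 3 reads "Has confluent central guttae in the study eye that can be removed by descemetorhexis", and the descemetorhexis takes place on Day -1, before the first dose. Safety and tolerability are a secondary objective, safety output is descriptive only, and sections 6.4 and 11.1.1 state that there is no safety or data monitoring committee. A table that is silent on worsening from a pre-dose grade would tell a reader less about ocular safety than its title suggests.

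**Working it through.** The plan gives no figure to reproduce, and the point concerns a definition. The check is a comparison of sections.

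**1. What each section does with worsening**

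| Protocol section | Applies to | New onset | Worsening of something already present |
|---|---|---|---|
| 6.3.2.1 | Adverse events | Counted | Counted (intensity or frequency) |
| 7.7.4.1 | AE tables | Counted | Not mentioned |
| 6.3.2.3 | AE recording | n/a | A change of intensity becomes a new, dated AE record |
| 7.7.4.5 | Slit-lamp and ophthalmoscopy grades | Counted | Not mentioned |
| 7.7.4.3 | Chemistry and haematology | n/a | Shift tables from baseline |

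The direct textual mismatch is between 6.3.2.1 and 7.7.4.1, since both concern adverse events. Section 6.3.2.3 largely closes it: "Any changes in intensity of signs and symptoms over multiple days will be captured by recording new AEs, with the amended intensity grades". An AE that intensifies on drug thus acquires a date after first treatment and passes the rule in 7.7.4.1. That repair covers intensity; it does not mention frequency, which 6.3.2.1 includes. For examination grades, the supplied documents contain neither the new-record rule that AEs have nor the shift table that laboratory values have.

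**2. How a patient is classified under 7.7.4.5**

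| Pre-dose grade | Worst post-dose grade | Onset = date the abnormality appeared | Onset = date it became CS |
|---|---|---|---|
| Normal | CS | Counted | Counted |
| NCS | CS | Left out | Counted |
| CS | CS | Left out | Left out |

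Only the middle row depends on the meaning of onset. The first reading is the plainer one, because the rule attaches the onset date to an abnormality and NCS is an abnormal grade. The second is possible, because the quantity counted is a CS abnormality. Two programmers could produce different tables from the same data and both cite the protocol.

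**3. Scale**

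The plan is approximately 60 patients randomised 1:1:1, so 60 / 3 = 20 per arm. One uncounted patient moves that arm's percentage by 1 / 20 = 5 percentage points. The documents give no basis for estimating how many eyes will go from NCS to CS.

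**4. Are pre-dose grades available?**

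Table 6-1 schedules slit-lamp evaluation at Visit 1, pre-operatively at Visit 2, and at Visit 3. Sections 3.1 and 5.2 have patients dose on Visit 3 only after all measurements are done. The last pre-dose slit-lamp grade is therefore normally the one taken the day after surgery.

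**The case against.** The strongest reply is that corneal worsening has other routes into the report. Section 6.3.2.1 lists "Exacerbation of a pre-existing disease or symptom" among possible AEs, 6.3.2.2 sends AEs identified from any study data to the AE page, 6.3.2.3 dates changes in intensity, and 7.7.4.1 summarises ocular TEAEs by arm with the study eye shown separately. Corneal thickness change, absence of oedema and corneal clearance are compared with placebo at each visit under 7.2 and 7.7.2. All slit-lamp data are listed. This stands, and it limits the point to one descriptive table. It does not remove it: none of these outputs summarises movement from NCS to CS by structure, eye and arm.

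A second reply is that 6.3.2.1 defines adverse events and does not govern examination grades. That is correct. A reader might infer that 7.7.4.5 contradicts 6.3.2.1. The documents support only that one term carries two meanings, with the direct mismatch lying in 7.7.4.1.

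A third is that the post-operative, pre-dose examination may itself be graded CS, and a rule that starts from it would then never count that eye. This also stands, and is why the shift table must start from Visit 1 as well.

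Finally, section 7.7 leaves data conventions to the SAP. The document supplied is an addendum that does not repeat primary SAP v2.0, so that version may already settle the matter.

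**Conclusion.** The point holds as a gap in definition with a low-cost remedy. Section 7.7.4.5 rests on an onset date that it does not define for examination findings and has no worsening limb. On its plain wording, an NCS finding that becomes CS on drug is left out of the only ocular-grade summary in the supplied documents. The size is 5 percentage points per uncounted patient at 20 per arm, with an unknown number of patients. The conclusion assumes that primary SAP v2.0 adds neither a worsening rule nor a shift table.

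Three stronger inferences are tempting and are not supported:

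- That worsening is certainly excluded. Onset could be read as the date the finding became CS.
- That all 60 study eyes are affected. The inclusion criteria show that each cornea is abnormal at entry, not that it is graded NCS. Some may be CS already, and the confluent guttae that qualify the eye are excised before dosing.
- That an arm with more corneal worsening would look the same as placebo. That could be true of this one table, but not of the AE tables and the corneal efficacy endpoints taken together.

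**What to change.** First check whether primary SAP v2.0 already defines onset for examination findings or includes an ocular shift table. If not, then in section 7.7.4.5 or the SAP:

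1. Replace the onset-date rule with a grade rule. An item is treatment-emergent CS if it is CS at any post-dose visit and was normal or NCS at the last examination before the first dose.
2. Add a normal/NCS/CS shift table by structure, eye and arm. Start it both from Visit 1 and from the last pre-dose examination, and run it to each visit and to the worst post-dose grade. The Visit 1 starting point keeps visible those eyes that are already CS on the day after descemetorhexis, which the rule in item 1 cannot count.
3. Align the onset-only wording of 7.7.4.1 with the new-or-worsened definition in 6.3.2.1.

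The slit-lamp grades needed are already scheduled. Table 6-1 as supplied shows no separate row for dilated ophthalmoscopy, so the sponsor should confirm which examination serves as its pre-dose reference. The cost is wording and one extra table. The counted rates may rise slightly, because some patients whom the present wording omits would be included.
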